14.1 Informed Consent Process

Informed consent is a process where information is presented to enable persons to voluntarily decide whether or not to participate as a research subject. It is an ongoing conversation between the human research subject and the researchers, which begins before consent is given and continues until the end of the subject's involvement in the research. Discussions about the research will provide essential information about the study and include purpose, duration,

experimental procedures, alternatives, risks, and benefits. Subjects will be given the opportunity to ask questions and have them answered.

The subjects will sign the informed consent document before undergoing any research procedures. The subjects may withdraw consent at any time throughout the course of the trial. A copy of the informed consent document will be given to the subjects for their records. The researcher will document the signing of the consent form in the subject's medical record. The rights and welfare of the subjects will be protected by emphasizing to them that the quality of their medical care will not be adversely affected if they decline to participate in this study.

14.1.1 Remote Consent Process

During the coronavirus disease 2019 pandemic, reconsent will be obtained remotely from the final enrolled participant.

The informed consent document will be sent via secure email or file transfer to the potential participant. An explanation of the study will be provided over the telephone or NIH-approved video conferencing platform (e.g., Zoom, Microsoft Teams) after the participant has had the opportunity to read the consent form. The participant can print the appropriate form to sign and date in ink, or they can sign and date digitally using a stylus or mouse.

The participant will return the signed and dated consent form to the consenting investigator, who will sign and date it with the date it was received. The consent form can either be printed and signed and dated in ink, or signed and dated digitally. A fully executed copy will be sent to the participant for their records.

The informed consent process will be documented on a progress note by the consenting investigator. The investigator will confirm that written consent has been obtained prior to initiating any study interventions.

14.2 Subject Confidentiality

Participant confidentiality and privacy is strictly held in trust by the participating investigators, their staff, and the sponsor. This confidentiality is extended to cover testing of biological samples in addition to the clinical information relating to participants. Therefore, the study protocol, documentation, data, and all records will be kept confidential to the extent provided by federal, state and local law. No information concerning the study or the data will be released to any unauthorized third party without prior written approval of the sponsor.

All research activities will be conducted in as private a setting as possible.

The study monitors and other authorized representatives of the Sponsor, representatives of the IRB, and/or regulatory agencies may inspect all documents and records required to be maintained by the Investigator, including but not limited to, medical records (office, clinic, or hospital) and pharmacy records for the participants in this study. The clinical study site will permit access to such records.

The study participant's contact information will be securely stored at the clinical site for internal use during the study. At the end of the study, all records will continue to be kept in a secure location for as long a period as dictated by the reviewing IRB, institutional policies, or Sponsor requirements.

Records will be kept locked and all computer entry and networking programs will be done with coded numbers only. Only investigators will have access to the code key. Clinical information will not be released without written permission of the subject, except as necessary for monitoring by the IRB, the FDA, NIAID, OHRP, or the sponsor's designee.

For subjects residing outside the local (Bethesda, MD) area, blood samples for safety labs (CBC with diff, Comprehensive BMP), may be drawn and processed at Quest Diagnostics, LabCorp, or by a primary care doctor. These samples may be labeled with a StudyID (i.e. Matinas MB70004), gender, and date of birth, as required by the local facility.

To further protect the privacy of study participants, a Certificate of Confidentiality has been issued by the NIH. This certificate protects identifiable research information from forced disclosure. It allows the investigator and others who have access to research records to refuse to disclose identifying information on research participation in any civil, criminal, administrative, legislative, or other proceeding, whether at the federal, state, or local level. By protecting researchers and institutions from being compelled to disclose information that would identify research participants, Certificates of Confidentiality help achieve the research objectives and promote participation in studies by helping assure confidentiality and privacy to participants.

15 Data Handling and Record Keeping

15.1 Data Capture and Management

Study data will be maintained in CRIMSON, and collected directly from subjects during study visits and telephone calls, or will be abstracted from subjects' medical records. Source documents include all recordings of observations or notations of clinical activities and all reports and records necessary to confirm the data abstracted for this study. Data entry into CRIMSON will be performed by authorized individuals. The Investigator is responsible for assuring that the data collected are complete, accurate, and recorded in a timely manner.

Appendix A Toxicity Table

NATIONAL INSTITUTE OF ALLERGY AND INFECTIOUS DISEASES, DIVISION OF MICROBIOLOGY AND INFECTIOUS DISEASES (DMID) ADULT TOXICITY TABLE (MODIFIED)

ABBREVIATIONS: Abbreviations utilized in the Table:

ULN = Upper Limit of Normal LLN = Lower Limit of

Normal

Rx = Therapy Req = Required

Mod = Moderate IV = Intravenous

ADL = Activities of Daily Living Dec = Decreased

ESTIMATING SEVERITY GRADE

For abnormalities NOT found elsewhere in the Toxicity Tables use the scale below to estimate grade of severity:

GRADE1 Mild: Transient or mild discomfort (<48 hours); no

medical intervention/therapy required

GRADE2 Moderate: Mild to moderate limitation in activity -

some assistance may be needed; no or minimal

medical intervention/therapy required

GRADE3 Severe: Marked limitation in activity, some

assistance usually required; medical

intervention/therapy required, hospitalizations

possible.

GRADE4 Life-threatening: Extreme limitation in activity,

significant assistance required; significant medical intervention/therapy required, hospitalization or

hospice care probable

SERIOUS OR LIFE-THREATENING AES

ANY clinical event deemed by the clinician to be serious or life-threatening should be considered a grade 4 event.

LABORATORY RANGES

Where discrepancies in the ULN and LLN of laboratory ranges occur between those included in this document and those of the laboratory that performs the assays, the values provided by the laboratory will be used for assignment of severity grade.

HEMATOLOGY					
	Grade 1	Grade 2	Grade 3	Grade 4	
Hemoglobin	9.5 - 10.5 gm/dL	8.0 - 9.4 gm/dL	6.5 - 7.9 gm/dL	< 6.5 gm/dL	
Absolute Neutrophil	1000-1500/mm ³	750-999/mm ³	500-749/mm ³	<500/mm ³	
Count					
Platelets	75,000-	50,000-	20,000-	<20,000/mm ³	
	99,999/mm ³	74,999/mm ³	49,999/mm ³		
WBCs	11,000-13,000/	13,000-15,000	15,000-	>30,000 or	
	mm ³	/mm ³	30,000/mm ³	<1,000 mm ³	
% Polymorphonuclear	> 80%	90 – 95%	>95%		
Leucocytes + Band					
Cells					
Activated Partial	1.01 -1.66 × ULN	1.67 - 2.33 ×	2.34 - 3 × ULN	> 3 × ULN	
Thromboplastin (APTT)		ULN			
CHEMISTRIES	1		1		
	Grade 1	Grade 2	Grade 3	Grade 4	

Hyponatremia	130-135 mEq/L	123-129 mEq/L	116-122 mEq/L	< 116 mEq/L or abnormal sodium with mental status changes or seizures
Hypernatremia	146-150 mEq/L	151-157 mEq/L	158-165 mEq/L	> 165 mEq/L or abnormal sodium with mental status changes or seizures
Hypokalemia	3.0 - 3.4 mEq/L	2.5 - 2.9 mEq/L	2.0 - 2.4 mEq/L or intensive replacement therapy or hospitalization required	< 2.0 mEq/L or abnormal potassium with paresis, ileus or life-threatening arrhythmia
Hyperkalemia	5.6 - 6.0 mEq/L	6.1 - 6.5 mEq/L	6.6 - 7.0 mEq/l	> 7.0 mEq/L or abnormal potassium with life-threatening arrhythmia
Hypoglycemia	55-64 mg/dL	40-54 mg/dL	30-39 mg/dL	<30 mg/dL or abnormal glucose with mental status changes or coma
Hyperglycemia (nonfasting and no prior diabetes)	116 - 160 mg/dL	161- 250 mg/dL	251 - 500 mg/dL	> 500 mg/dL or abnormal glucose with ketoacidosis or seizures
Hypocalcemia(corrected for albumin)	8.4 - 7.8 mg/dL	7.7 - 7.0 mg/dL	6.9 - 6.1 mg/dL	< 6.1 mg/DI or abnormal calcium with life threatening arrhythmia or tetany

Hypercalcemia (correct	10.6 - 11.5 mg/dL	11.6 -	12.6 - 13.5 mg/dL	> 13.5 mg/dL or
for albumin)		12.5 mg/dL	3	abnormal calcium with life threatening arrhythmia
Hypomagnesemia	1.4 - 1.2 mEq/L	1.1 - 0.9 mEq/L	0.8 - 0.6 mEq/L	< 0.6 mEq/L or abnormal magnesium with life-threatening arrhythmia
Hypophosphatemia	2.0 - 2.4 mg/dL	1.5 -1.9 mg/dL or replacement Rx required	1.0 -1.4 mg/dL intensive therapy or hospitalization required	< 1.0 mg/dL or abnormal phosphate with life-threatening arrhythmia
Hyperbilirubinemia (when accompanied by any increase in other liver function test)	1.1 - <1.25 x ULN	1.25 - <1.5 x ULN	1.5 – 1.75 x ULN	> 1.75 x ULN
Hyperbilirubinemia (when other liver function are in the normal range)	1.1 - <1.5 x ULN	1.5 - <2.0 x ULN	2.0 – 3.0 x ULN	> 3.0 x ULN
BUN	1.25 - 2.5 x ULN	2.6 - 5 x ULN	5.1 - 10 x ULN	> 10 x ULN
Hyperuricemia (uric acid)	7.5 – 10.0 mg/dL	10.1 – 12.0 mg/dL	12.1 – 15.0 mg/dL	>15.0 mg/dL
Creatinine	1.1 - 1.5 x ULN	1.6 - 3.0 x ULN	3.1 - 6 x ULN	> 6 x ULN or dialysis required
ENZYMES	1	1	1	1
	Grade 1	Grade 2	Grade 3	Grade 4
AST (SGOT)	1.1 - <2.0 x ULN	2.0 – <3.0 x ULN	3.0 – 8.0 x ULN	> 8 x ULN

ALT (SGPT)	1.1 - <2.0 x ULN	2.0 – <3.0 x	3.0 – 8.0 x ULN	> 8 x ULN
		ULN		
Alkaline Phosphatase	1.1 - <2.0 x ULN	2.0 – <3.0 x	3.0 – 8.0 x ULN	> 8 x ULN
		ULN		
URINALYSIS		l		I
	Grade 1	Grade 2	Grade 3	Grade 4
Proteinuria	1+ or 200 mg - 1	2-3+ or 1- 2 gm	4+ or 2-3.5 gm	nephrotic
	gm loss/day	loss/day	loss/day	syndrome
				or
				> 3.5 gm loss/day
Hematuria	microscopic only	gross, no clots	gross, with or	obstructive or
	.40 " 6		without clots, OR	required
	<10 rbc/hpf	>10 rbc/hpf	red blood cell casts	transfusion
CARDIOVASCULAR		1		
	Grade 1	Grade 2	Grade 3	Grade 4
Cardiac Rhythm		asymptomatic,	recurrent/persistent	unstable
		transient signs,	symptomatic Rx	dysrhythmia;
		no Rx required	required	hospitalization
				and treatment
				required
Hypertension	transient increase	recurrent,	acute treatment	end organ
		chronic	required;	damage or
	> 20 mm/Hg; no	increase	outpatient	hospitalization
	treatment	> 20/1	treatment or	required
		> 20mm/Hg.	hospitalization	
		/treatment	possible	
		required		

Hypotension	transient	symptoms due	requires IV fluids;	mean arterial
	orthostatic	to orthostatic	no hospitalization	pressure
	hypotension with	hypotension or	required	
	heart rate	BP decreased		<60mm/ Hg or
	increased by <20	by <20 mm Hg		end organ
	beat/min or	systolic;		damage or shock;
	decreased by <10	correctable with		requires
	mm Hg systolic BP,	oral fluid		hospitalization
	No treatment	treatment		and vasopressor
	required			treatment
Pericarditis	minimal effusion	mild/moderate	symptomatic	tamponade;
		asymptomatic	effusion; pain;	pericardiocentesis
		effusion, no	EKG changes	or surgery
		treatment		required
Hemorrhage, Blood	microscopic/occult	mild, no	gross blood loss;	massive blood
Loss		transfusion		loss; > 3 units
			1-2 units	transfused
			transfused	
RESPIRATORY				
	Grade 1	Grade 2	Grade 3	Grade 4
Cough	transient- no	persistent	Paroxysmal cough;	
	treatment	cough;	uncontrolled with	
			treatment	
		treatment		
		responsive		
Bronchospasm, Acute	transient; no	requires	no normalization	cyanosis: FEV ₁
	treatment;	treatment;	with	. 050/
	700/ 000/ 55\/	normalizes with	bronchodilator;	< 25%
	70% - 80% FEV ₁	bronchodilator;	FEV 050/ 500/	of peak flow or
	of peak flow	FEV 500/	FEV ₁ 25% - 50%	intubation
	or pour now	FEV ₁ 50% -	of peak flow; or	necessary
		70%	retractions present	l looosai y
		(of peak flow)	Totactions present	
Dyspnea	dyspnea on	dyspnea with	dyspnea at rest	Dyspnea
	exertion	normal activity		requiring oxygen
				therapy

GASTROINTESTINAL				
	Grade 1	Grade 2	Grade 3	Grade 4
Nausea	mild or transient; maintains reasonable intake	moderate discomfort; intake decreased significantly; some activity limited	no significant intake; requires IV fluids	hospitalization required;
Vomiting	1 episode in 24 hours	2-5 episodes in 24 hours	>6 episodes in 24 hours or needing IV fluids	physiologic consequences requiring hospitalization or requiring parenteral nutrition
Constipation	requiring stool softener or dietary modification	requiring laxatives	obstipation requiring manual evacuation or enema	obstruction or toxic megacolon
Diarrhea	mild or transient; 3- 4 loose stools/day or mild diarrhea last < 1 week	moderate or persistent; 5-7 loose stools/day or diarrhea lasting >1 week	>7 loose stools/day or bloody diarrhea; or orthostatic hypotension or electrolyte imbalance or >2L IV fluids required	hypotensive shock or physiologic consequences requiring hospitalization
Oral Discomfort/Dysphagia	mild discomfort; no difficulty swallowing	some limits on eating/drinking	eating/talking very limited; unable to swallow solid foods	unable to drink fluids; requires IV fluids

NEUROLOGICAL				
	Grade 1	Grade 2	Grade 3	Grade 4
Neuro-Cerebellar	slight incoordination dysdiadochokinesis	intention tremor, dysmetria, slurred speech; nystagmus	locomotor ataxia	Incapacitated
Psychiatric	mild anxiety or depression	moderate anxiety or depression; therapy required; change in normal routine	severe mood changes requiring therapy; or suicidal ideation; or aggressive ideation	acute psychosis requiring hospitalization; or suicidal gesture/attempt or hallucinations
Muscle Strength	subjective weakness, no objective symptoms/ signs	mild objective signs/symptoms no decrease in function	objective weakness function limited	Paralysis
Paresthesia (burning, tingling, etc.)	mild discomfort; no treatment required	moderate discomfort; non- narcotic analgesia required	severe discomfort; or narcotic analgesia required with symptomatic improvement	incapacitating; or not responsive to narcotic analgesia
Neuro-sensory	mild impairment in sensation (decreased sensation, e.g. vibratory, pinprick, hot/cold in great toes) in focal area or symmetrical distribution; or change in taste, smell, vision and/or hearing	moderate impairment (mod decreased sensation, e.g. vibratory, pinprick, hot/cold to ankles) and/or joint position or mild impairment that is not symmetrical	severe impairment (decreased or loss of sensation to knees or wrists) or loss of sensation of at least mod degree in multiple different body areas (i.e. upper and lower extremities)	sensory loss involves limbs and trunk; paralysis; or seizures

	Grade 1	Grade 2	Grade 3	Grade 4
Arthralgia (joint pain)	mild pain not interfering with function	moderate pain, analgesics and/or pain interfering with function but not with activities of daily living	severe pain; pain and/or analgesics interfering with activities of daily living	disabling pain
Arthritis	mild pain with inflammation, erythema or joint swelling – but not interfering with function	moderate pain with inflammation, erythema or joint swelling – interfering with function, but not with activities of daily living	severe pain with inflammation, erythema or joint swelling –and interfering with activities of daily living	permanent and/ordisabling joint destruction
Myalgia	Myalgia with no limitation of activity	muscle tenderness (at other than injection site) or with moderate impairment of activity	severe muscle tenderness with marked impairment of activity	frank myonecrosis

SKIN				
	Grade 1	Grade 2	Grade 3	Grade 4
Mucocutaneous	erythema; pruritus	diffuse, maculo papular rash, dry desquamation	vesiculation or moist desquamation or ulceration	exfoliative dermatitis, mucous membrane involvement or erythema, multiforme or suspected Stevens-Johnson or necrosis requiring surgery
Induration	< 15mm	15-30 mm	>30mm	
Erythema	< 15mm	15-30 mm	>30mm	
Edema	< 15mm	15-30 mm	>30mm	
Rash at Injection Site	< 15mm	15-30 mm	>30mm	
Pruritus	slight itching at injection site	moderate itching at injection extremity	itching over entire body	
SYSTEMIC				
	Grade 1	Grade 2	Grade 3	Grade 4
Allergic Reaction	pruritus without rash	localized urticaria	generalized urticaria; angioedema	Anaphylaxis
Headache	mild, no treatment required	transient, moderate; treatment required	severe; responds to initial narcotic therapy	intractable; requires repeated narcotic therapy

CAMB for CMC Protocol Version 17.0 May 1,2021

Fever: oral	37.7 - 38.5° C or	38.6 - 39.5 °C	39.6 - 40.5 °C or	> 40 °C or > 105
	100.0 - 101.5 °F	or 101.6 - 102.9	103 - 105 °F	°F
		°F		
Fatigue	normal activity	normal activity	normal activity	unable to care for
	reduced < 48 hours	decreased 25-	decreased > 50%	self
		50% > 48 hours	can't work	

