11.7 Stopping Rules for an Individual Subject

A study subject will be discontinued from further study agent administration in the event of 1 or more of the following:

- Gastrointestinal toxicity (nausea/vomiting/diarrhea) that is interfering with the ability to perform regular every day activities.
- A subject experiences two Grade 3 events and/or one Grade 4 event that is possibly, probably, or definitely related to participation in the trial;
- SAE that is possibly, probably or definitely related to the study drug.
- Any laboratory abnormality, intercurrent illness, other medical condition or situation that occurs such that continued participation in the study would not be in the best interest of the subject.
- Any other events that the patient or investigators deems of clinical significance.

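### Appendix A gives some values two grades, and one value none, where the stopping, pausing and extension-entry rules act; a related fever of 40.1–40.5 °C alone decides whether discontinuation is mandatory

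*Combined protocol and SAP*

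**What the plan says.** Section 11.1 adopts the modified DMID adult table in Appendix A as the toxicity scale. Three rules act on its grades:

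- Section 11.7 ends study drug if "A subject experiences two Grade 3 events and/or one Grade 4 event that is possibly, probably, or definitely related to participation in the trial".
- Section 6.6 requires, for extension entry, that the same related-event counts have not been reached.
- Section 11.6 pauses dosing for a Grade 3 laboratory event considered at least possibly related.

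Under Section 11.10.1 the safety monitoring committee is told at once when a pausing or stopping rule is met.

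The relevant rows of Appendix A are:

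- Fever: Grade 3 is 39.6–40.5 °C or 103–105 °F. Grade 4 is above 40 °C or above 105 °F.
- Hematuria: Grade 2 is "gross, no clots". Grade 3 is gross, with or "without clots, OR" red blood cell casts.
- WBC: Grade 2 is 13,000–15,000/mm³ and Grade 3 is 15,000–30,000/mm³.
- Proteinuria: Grade 2 includes 1–2 g/day and Grade 3 includes 2–3.5 g/day.
- Vomiting: Grade 2 is "2-5 episodes in 24 hours" and Grade 3 is ">6 episodes in 24 hours or needing IV fluids".

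**The concern.** A table that drives mandatory actions has to map each value to one grade. Here the overlaps and the gap sit at the Grade 2/3 and 3/4 boundaries, which are the ones the rules use. Two graders following the protocol correctly can therefore reach different grade-based actions for the same event. At stake are whether a participant permanently loses a drug that may be helping, whether that participant may enter the extension, and whether the safety monitoring committee is notified. Vomiting is also among the side effects Section 8.1 reports for this drug.

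**Working it through.** The plan states no figure on this point to reproduce. The check puts each value into the printed ranges, then takes the resulting grade through the rules.

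**Step 1: fever units.** Formula: °F = 9/5 × °C + 32.

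- 40.0 °C: 72.0 + 32 = 104.0 °F
- 40.1 °C: 72.18 + 32 = 104.2 °F
- 40.5 °C: 72.9 + 32 = 104.9 °F
- In reverse, 105 °F: (105 − 32) × 5/9 = 40.56 °C

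So 40.1–40.5 °C equals 104.2–104.9 °F, which is Grade 3 only in Fahrenheit but Grades 3 and 4 in Celsius. The Grade 3 upper limits (40.5 °C, 105 °F) and the Grade 4 Fahrenheit limit (above 105 °F) agree to rounding. The Grade 4 Celsius limit of 40 °C is the one out of line.

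**Step 2: grades for each value, and what follows if the event is related.**

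| Value | Grades that fit | Grade-based result |
|---|---|---|
| Fever 40.1–40.5 °C | 3 and 4 | Grade 4: drug stopped (11.7), extension barred (6.6). A single Grade 3: neither, and no pause, because fever is not a laboratory event |
| Gross hematuria, no clots | 2 and 3 | Grade 3: pause under 11.6 if a laboratory event, and one toward two Grade 3 events. Grade 2: neither |
| WBC 15,000/mm³ | 2 and 3 | As for hematuria; plainly a laboratory event |
| Proteinuria 2 g/day | 2 and 3 | As for WBC |
| Vomiting, 6 episodes, no IV fluids | none (5 is Grade 2, 7 is Grade 3) | Counts toward two Grade 3 events, or does not |

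Hematuria is listed under the urinalysis block of Appendix A, which makes the laboratory reading plausible, but Section 11.6 does not define the term. The proteinuria overlap arises only for a quantified daily loss; the dipstick categories in the same row (2–3+ and 4+) do not overlap.

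**Step 3: is there a tie-break?** Appendix A opens with three general provisions. The fallback severity scale covers only abnormalities absent from the table. The laboratory-range paragraph deals only with differing normal limits. The remaining sentence raises an event to Grade 4 when the clinician judges it serious or life-threatening, which does not choose between two printed grades for other events. None says which grade to use when two fit.

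**The case against.** The strongest reply is that grade is not the only trigger. Section 5.3.2 suspends treatment for toxicity attributed to the drug, gastrointestinal symptoms included, whatever the grade. Section 11.6 allows a pause for any safety issue. Section 11.7 stops for gastrointestinal toxicity that interferes with daily activities, and leaves room for the patient's or investigator's judgement. This stands. A reader might infer that an event in these bands could pass with no consequence; the documents do not support that. For hematuria in particular, Section 5.3.2 suspends dosing at either grade. It does not remove the fever contradiction, because suspension under 5.3.2 allows re-initiation and a related Grade 4 event does not.

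Three other inferences fail:

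- *Hypokalemia needing hospitalization is Grade 3 in its row but Grade 4 as a serious event.* Appendix A does say "ANY clinical event deemed by the clinician to be serious or life-threatening should be considered a grade 4 event", but that rests on a clinician's judgement. A related serious event already stops the drug (11.7) and bars extension (6.6), so neither action changes.
- *Generalised itching is graded differently under Allergic Reaction and Pruritus.* These are separate rows, and a single Grade 3 itch triggers no grade-based rule.
- *One re-graded patient in 16 moves the treatment-limiting toxicity rate by 1/16.* Section 3.2.2 does not define that endpoint by grade, and the safety denominator is everyone dosed, with replacements and a ceiling of 20.

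It is also fair to say that enrollment is closed, so most extension-entry decisions may be past, and that choosing cut points after open-label data have been seen invites bias. The first narrows the benefit to the stopping and pausing rules during extension dosing of up to 60 months. The second is met by taking the cut points from the table's own adjacent limits.

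**Conclusion.** The point holds in a limited form: for these values the grade-based consequence is contradictory or undefined, while the grade-independent rules remain in force. Fever of 40.1–40.5 °C is the only one where a single related event decides mandatory discontinuation and extension entry by grade alone. For hematuria without clots, WBC of exactly 15,000/mm³ and proteinuria of exactly 2 g/day, the laboratory pause and the Grade 3 count are contradictory. Six vomiting episodes matter only as one of two Grade 3 events. The halting rule and the nephrotoxicity and hypokalemia endpoints use their own numeric limits and are unaffected.

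This assumes that the table as printed is the one graders use, that the event is judged at least possibly related, that hematuria counts as a laboratory event for the pause, and that some participants are still on extension dosing. The documents give no frequency of events in these bands, so no rate can be attached.

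**What to change.** Edit five rows of Appendix A:

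- Fever: Grade 4 above 40.5 °C (above 105 °F), matching the Grade 3 upper limits. Name the unit that governs, since 105 °F is 40.56 °C and a small rounding difference remains.
- Hematuria: Grade 3 limited to gross with clots, or red blood cell casts.
- WBC: Grade 3 above 15,000/mm³.
- Proteinuria: Grade 3 above 2 g/day.
- Vomiting: Grade 3 at 6 or more episodes.

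Alternatively, add one sentence that the higher grade applies when a value fits two. That is more cautious, since it puts fever above 40 °C in Grade 4, but it does not fill the vomiting gap, so the vomiting edit is still needed.

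Apply the change to ongoing extension participants and re-grade every recorded event in these bands, keeping the grade first assigned on record beside the new one. The cost is a short amendment and limited re-grading.
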